4.1 TREATMENT PLAN

4.1 Treatment Dosage and Administration

Regorafenib 80 mg QD Week 1/120 mg QD Week 2/160 mg QD Week 3 then 1 week off followed by Cycle 2+ 160 mg QD D1-21, of a 28 day cycle.

Regorafenib tablets should be taken in the morning with approximately 8 fluid ounces (240 mL) of water after a low-fat (<30% fat) breakfast. Some examples of low fat breakfasts are:

- Two slices of white toast with 1 tablespoon of low-fat margarine and 1 tablespoon of jelly and 8 ounces (240 mL) of skim milk (approximately 319 calories and 8.2 g of fat).
- One cup of cereal (i.e. Special K), 8 ounces (240 mL) of skim milk, one piece of toast with jam (no butter or marmalade), apple juice, and one cup of coffee or tea (2 g fat, 17 g

protein, 93 g of carbohydrate, 520 calories.

4.2 Toxicities and Dosing Delays/Dose Modifications

Any patient who receives treatment on this protocol will be evaluable for toxicity. Each patient will be assessed for the development of toxicity according to the Study Calendar. Toxicity will be assessed according to the NCI Common Terminology Criteria for Adverse Events (CTCAE), version 4.0. Dose adjustments should be made according to the system showing the greatest degree of toxicity.

4.2.1.1 Dose Levels and Reductions

Study medication will be administered on a 3 weeks on/1week off schedule [3 weeks out of every 4]. A new cycle of therapy can start when all toxicities, (except hand-foot syndrome, alopecia, non-refractory nausea/vomiting, non-refractory hypersensitivity and nonclinical and asymptomatic laboratory abnormalities) have resolved to Grade 2 or less. Hand-foot syndrome must have resolved to Grade 0-1.

Doses will be delayed or reduced for clinically significant hematologic and non-hematologic toxicities that are related to protocol therapy according to the guidelines shown in the Dose Delays/Dose Modifications table that follows. Dose modifications will follow predefined dose levels. Dose adjustments for hematologic toxicity are based on the blood counts obtained in preparation for the day of treatment.

Strictly follow the modification in the following tables for the first **two** cycles until individual treatment tolerance can be ascertained. Thereafter, these modifications should be regarded as guidelines to produce mild-to-moderate, but not debilitating, side effects. If multiple adverse events are seen, administer dose based on greatest reduction required for any single adverse event observed. Reductions or increases apply to treatment given in the preceding cycle and are based on adverse events observed since the prior dose.

Dose Level			If no SDRT	If + SDRT**
Dose level 0*	80 mg po qd	Two 40-mg tablets of regorafenib	Proceed to next dose level	
Dose level 1	120 mg po qd	Three 40-mg tablets of regorafenib	Proceed to next dose level	Decrease to 80 mg
Dose level 2	160 mg po qd	Four 40-mg tablets of regorafenib		Decrease to 120 mg
* Starting Dose				
** SDRT= Significant Drug Related Toxicities				

If a subject experience more than one toxicity, dose reduction should be according to the toxicity with the highest grade

In the case of two or more toxicities of the same grade, the investigator may dose reduce according to that deemed most causally related to study treatment

The following tables outline dose adjustments for toxicities related to study drug except hand-foot skin reaction, hypertension and liver function test abnormalities.

NCI-CTCAE v4.0 ^a	Dose Interruption	Dose Modification ^b	Dose for Subsequent Cycles
Grade 0-2	Treat on time	No change	No change
Grade 3	Delay until \leq Grade 2 ^c	Reduce by 1 dose level	If toxicity remains < Grade 2, dose re-escalation can be considered at the discretion of the treating investigator. If dose is re-escalated and toxicity (\geq Grade 3) recurs, institute permanent dose reduction.
Grade 4	Delay until \leq Grade 2 ^c	Reduce by 1 dose level. Permanent discontinuation can be considered at treating investigator's discretion.	

- a. NCI-CTCAE = National Cancer Institute - Common Terminology Criteria for Adverse Events, version 4.0
- b. Excludes alopecia, non-refractory nausea/vomiting, lymphocyte count decreased, non-refractory hypersensitivity and nonclinical and asymptomatic laboratory abnormalities.
- c. If no recovery after a 4 week delay, treatment should be permanently discontinued unless subject is deriving clinical benefit.

The table above outlines dose adjustments for hematologic and non-hematologic toxicities related to regorafenib except HFSR and hypertension.

In addition to these recommended dose modifications, subjects who develop diarrhea, mucositis, anorexia or other events predisposing to fluid loss or inadequate fluid intake should be carefully monitored and rehydrated as clinically necessary. This is in order to minimize the risk of postural hypotension and renal failure.

	Grade 1	Grade 2	Grade 3
NCI-CTCAE v4.0 Palmar-plantar erythrodysesthesia syndrome ^a	Minimal skin changes or dermatitis (e.g., erythema, edema, or hyperkeratosis) without pain	Skin changes (e.g., peeling, blisters, bleeding, edema, or hyperkeratosis) with pain	Severe skin changes (e.g., peeling, blisters, bleeding, edema, or hyperkeratosis) with pain
Further description / examples of skin changes	Numbness, dysesthesia/paresthesia tingling, painless swelling, or erythema of the hands and/or feet	Painful erythema and swelling of the hands and/or feet	Moist desquamation, ulceration, blistering, or severe pain of the hands and/or feet
Effect on activities	Does not disrupt normal activities	Limiting instrumental activities of daily life (e.g., preparing meals, shopping for groceries or clothes, using the telephone, managing money)	Limiting self-care activities of daily life (e.g., bathing, dressing and undressing, feeding self, using the toilet, taking medications) and not bedridden
a. Palmer-planter erythrodysesthesia syndrome is a disorder characterized by redness, marked discomfort, swelling, and tingling in the palms of hands or the soles of the feet.			

Table 3 Recommended dose modification for hand-foot-skin reaction (HFSR)^a

Grade of event (NCI-CTCAE v4.0)	Occurrence	Suggested Dose Modification
Grade 1	Any	Maintain dose level and immediately institute supportive measures for symptomatic relief

Grade 2	1 st occurrence	Consider decreasing dose by one dose level and immediately institute supportive measures. If no improvement, interrupt therapy for a minimum of 7 days, until toxicity resolves to Grade 0-1 ^{b,c}
	No improvement within 7 days or 2 nd occurrence	Interrupt therapy until toxicity resolves to Grade 0-1. ^c When resuming treatment, treat at reduced dose level ^b
	3 rd occurrence	Interrupt therapy until toxicity resolves to Grade 0-1. ^c When resuming treatment, decrease dose by one dose level. ^{b,d}
	4 th occurrence	Discontinue therapy
Grade 3	1 st occurrence	Institute supportive measures immediately. Interrupt therapy for a minimum of 7 days until toxicity resolves to Grade 0-1. ^c When resuming treatment, decrease dose by one dose level. ^{b,d}
	2 nd occurrence	Institute supportive measures immediately. Interrupt therapy for a minimum of 7 days until toxicity resolves to Grade 0-1. ^c When resuming treatment, decrease dose by one additional dose level ^{b,d}
	3 rd occurrence	Discontinue treatment permanently.

a. More conservative management is allowed if judged medically appropriate by the investigator.
 
b. If toxicity returns to Grade 0-1 after dose reduction, dose re-escalation is not permitted.
 
c. If there is no recovery after a 4-week delay, treatment with regorafenib will be discontinued permanently.
 
d. Subjects requiring > 2 dose reductions should go off protocol therapy.
 
e. The maximum daily dose is 160 mg.
		

At first occurrence of HFSR, independent of grade, prompt institution of supportive measures such as topical emollients, low potency steroids, or urea-containing creams should be administered.

Recommended prevention/management strategies for skin toxicities consistent with HFSR are summarized below:

Control of calluses

Before initiating treatment with regorafenib:

- Check condition of hands and feet.
- Suggest a manicure/pedicure, when indicated.
- Recommend pumice stone use for callus or 'rough spot' removal.
- During regorafenib treatment:
 - Avoid pressure points.

- Avoid items that rub, pinch or create friction.

Use of creams

- Non-urea based creams may be applied liberally.
- Keratolytic creams (e.g. urea-based creams, salicylic acid 6%) may be used sparingly and only to affected (hyperkeratotic) areas.
- Alpha hydroxyl acids (AHA) based creams may be applied liberally 2 times a day. Approximately 5% to 8% provides gentle chemical exfoliation.
- Topical analgesics (e.g. lidocaine 2%) are to be considered for pain control.
- Topical corticosteroids like clobetasol 0.05% should be considered for subjects with Grade 2 or 3 HFSR. Avoid systemic steroids.

Tender areas should be protected as follows:

- Use socks/gloves to cover moisturizing creams
- Wear well-padded footwear
- Use insole cushions or inserts (e.g. silicon, gel)
- Foot soaks with tepid water and Epson salts

Hypertension

Hypertension is a known AE associated with regorafenib treatment. Subject will have their blood pressure measured at least weekly at the study site during the first 6 weeks of treatment. If additional blood pressure measurements are done outside the study site, and the blood pressure is > 140 mm Hg systolic or > 90 mm Hg diastolic (NCI CTCAE v4.0), then the subject must contact study personnel. The management of hypertension, including the choice of antihypertensive medication, will be performed according to local standards and to the usual practice of the investigator. Every effort should be made to control blood pressure by medical means other than study drug dose modification. If necessary, Table 4 outlines suggested dose reductions.

Table 4: Management of Treatment-Emergent Hypertension		
Grade of event (CTCAE v4.0)	Antihypertensive Therapy	Regorafenib Dosing
Grade 1 Prehypertension (systolic BP 120 - 139 mmHg or diastolic BP 80 - 89 mmHg)	None	
 • Continue regorafenib • Consider increasing blood pressure (BP) monitoring

Grade 2 Systolic BP 140 - 159 mmHg or diastolic BP 90 - 99 mmHg, OR Symptomatic increase by > 20 mmHg (diastolic) if previously within normal limits
	
 • Treat with the aim to achieve diastolic BP \leq 90 mm Hg: • If BP previously within normal limits, start anti-hypertensive monotherapy • If patient already on anti-hypertensive medication, titrate up the dose. 	
 • Continue regorafenib • If symptomatic, hold regorafenib until symptoms resolve AND diastolic BP \leq 90 mm Hg^a. When regorafenib is restarted, continue at the same dose level.

Grade 3 Systolic BP \geq 160 mmHg or diastolic BP \geq 100 mmHg OR More than one drug or more intensive therapy than previously used indicated
	
Treat with the aim to achieve diastolic BP \leq 90 mm Hg: Start anti-hypertensive medication
 
AND/OR Increase current anti-hypertensive medication
 
AND/OR Add additional anti-hypertensive medications.
	
 • Hold regorafenib until diastolic BP \leq 90 mm Hg, and if symptomatic, until symptoms resolve.^a • When regorafenib is restarted, continue at the same dose level. • If BP is not controlled with the addition of new or more intensive therapy, reduce by 1 dose level.^b • If Grade 3 hypertension recurs despite dose reduction and antihypertensive therapy, reduce another dose level.^c

Grade 4 Life-threatening consequences (eg, malignant hypertension, transient or permanent neurologic deficit, hypertensive crisis)
	
Per institutional guidelines
	
Discontinue therapy

a. Patients requiring a delay of >4 weeks should go off protocol therapy b. If BP remains controlled for at least one cycle, dose re-escalation permitted per investigator's discretion. c. Patients requiring >2 dose reductions should go off protocol therapy.
		

Liver Function Abnormalities

For patients with observed worsening of serum liver tests considered related to regorafenib (i.e. where no alternative cause is evident, such as post-hepatic cholestasis or disease progression), the dose modification and monitoring advice in Table 5 should be followed.

Regorafenib is a UGT1A1 inhibitor. Mild, indirect (unconjugated) hyperbilirubinemia may occur in patients with Gilbert's syndrome.

Table 5: Recommended measures and dose modifications in case of drug-related liver function

test abnormalities		
Observed elevations of ALT and/or AST	Occurrence	Recommended measures and dose modification

≤ 5 times upper limit of normal (ULN) (maximum Grade 2)	Any occurrence	Continue Regorafenib treatment. Monitor liver function weekly until transaminases return to < 3 times ULN (Grade 1) or baseline.
>5 times ULN to ≤ 20 times ULN (Grade 3)	1 st occurrence	Interrupt Regorafenib treatment. Monitor transaminases weekly until return to < 3 times ULN or baseline. Restart: If the potential benefit outweighs the risk of hepatotoxicity, re-initiate Regorafenib treatment, reduce dose by 40 mg (one tablet), and monitor liver function weekly for at least 4 weeks.
	Re-occurrence	Discontinue treatment with Regorafenib permanently.
>20 times ULN (Grade 4)	Any occurrence	Discontinue treatment with Regorafenib permanently.
>3 times ULN (Grade 2 or higher) with concurrent bilirubin >2 times ULN	Any occurrence	Discontinue treatment with Regorafenib permanently. Monitor liver function weekly until resolution or return to baseline. Exceptions: patients with Gilbert's syndrome who develop elevated transaminases should be managed as per the above outlined recommendations for the respective observed elevation of ALT and/or AST.
Weekly LFT monitoring for the first two cycles is required.		

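### Section 4.2.1.1 gives liver values holding and restarting rules that do not agree, and leaves unclear whether silent blood-count abnormalities are exempt

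*Combined protocol and SAP*

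**What the plan says.** All the text is in protocol section 4.2.1.1, which runs through to Table 5.

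- **Cycle-start sentence.** A new cycle can begin when toxicities, other than a list of exceptions, have settled. The list ends "non-refractory hypersensitivity and nonclinical and asymptomatic laboratory abnormalities) have resolved to Grade 2 or less". Hand-foot syndrome is also on the list, but the next sentence gives it its own threshold (Grade 0-1). Laboratory values get no threshold and no pointer to Table 5.
- **Next paragraph.** "Doses will be delayed or reduced for clinically significant hematologic and non-hematologic toxicities that are related to protocol therapy", and "Dose adjustments for hematologic toxicity are based on the blood counts obtained in preparation for the day of treatment".
- **General toxicity table.** The sentence introducing it takes hand-foot skin reaction, hypertension and liver function test abnormalities out of its scope. The sentence after it reads "The table above outlines dose adjustments for hematologic and non-hematologic toxicities related to regorafenib except HFSR and hypertension". The Grade 3 and Grade 4 rows delay treatment to Grade 2 or lower and drop one dose level. At Grade 4 the investigator may also consider stopping for good. Footnote b is attached to one column heading, "Dose Modification ^b", and reads "Excludes alopecia, non-refractory nausea/vomiting, lymphocyte count decreased, non-refractory hypersensitivity and nonclinical and asymptomatic laboratory abnormalities". The Dose Interruption column carries footnote c but not footnote b.
- **Table 5.** For a first drug-related ALT/AST above 5 and up to 20 x ULN: "Interrupt Regorafenib treatment. Monitor transaminases weekly until return to < 3 times ULN or baseline". A recurrence, or any value above 20 x ULN, means permanent discontinuation. Values up to 5 x ULN are labelled at most Grade 2. None of these rows depends on symptoms.

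**The concern.** Most liver-test and blood-count toxicities show first as laboratory results, so an exemption for laboratory abnormalities needs clear limits when the rules around it are triggered by laboratory results. Here it has none, and the liver rules differ from one another in scope and in restart threshold. Two investigators with the same ALT could each cite section 4.2.1.1, one to start the next cycle and one to hold.

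What is at stake is patient safety, and after that consistent dose intensity and toxicity reporting across the two centers. The question can arise at any cycle start, because section 5.2 schedules hematology and chemistries before each cycle and liver tests on Days 8, 15 and 22 of Cycles 1 and 2. Sites are told to follow the tables strictly in the first two cycles, which leaves little discretion when the conflict first appears.

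**Working it through.** There is no plan figure to reproduce. The check sets the rules side by side for three cases.

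**1. Does the general table cover liver tests?** Take a drug-related ALT or AST above 20 x ULN (Grade 4).

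| Scope sentence followed | General table applies? | Instruction |
|---|---|---|
| Before the table | No | Table 5 only: permanent discontinuation |
| After the table | Yes | General table: delay to Grade 2 or lower, reduce one level, discontinuation optional. Table 5: permanent discontinuation |

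Under the second sentence the same result carries two different instructions.

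**2. When may an interrupted patient restart?** Take a first ALT/AST above 5 and up to 20 x ULN, now falling, without the concurrent bilirubin rise that has its own row in Table 5.

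- Cycle-start test: Grade 2 or less, which in Table 5's grading is ALT/AST ≤ 5 x ULN.
- Table 5 test: ALT/AST < 3 x ULN, or baseline.
- Values passing the first but not the second: 3 x ULN ≤ ALT/AST ≤ 5 x ULN, a band 5 - 3 = 2 x ULN wide, unless the value is baseline.

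The baseline exception can be sized from section 3.1.7, assuming that baseline is the value at eligibility. Without liver involvement the entry limit is 2.5 x ULN. Since 2.5 < 3, baseline cannot lie in the band and the whole band is in dispute. With liver involvement the entry limit is 5 x ULN, so baseline may lie in the band, and only values above the patient's own baseline are in dispute.

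This mismatch does not depend on how the laboratory exemption is read. If a value still above 5 x ULN is also called nonclinical and asymptomatic, the cycle-start sentence permits a start where Table 5 interrupts. That further step does depend on undefined words.

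A patient who never exceeded 5 x ULN is not affected by the restart mismatch, because Table 5 then continues treatment as well.

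**3. Silent Grade 3 or 4 blood count, not lymphocytes.**

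| Rule | If nonclinical and asymptomatic | If clinically significant |
|---|---|---|
| Cycle-start sentence | Cycle may start | Wait for Grade 2 or less |
| Dose Interruption column | Delay to Grade 2 or less | Delay to Grade 2 or less |
| Dose Modification column with footnote b | No reduction | Reduce one level |

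The right-hand column is consistent. The left-hand column is not. At 160 mg the possible restarts are 160 mg on time, 160 mg after a delay, or 120 mg after a delay; (160 - 120)/160 = 25% less per day. Optional discontinuation is also open at Grade 4. The delay is not capped at four weeks, because footnote c lets a patient with clinical benefit continue.

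The separate entry for lymphocytes in footnote b would be largely redundant if all silent counts were exempt, which hints that other counts were not meant to be. No sentence says so.

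**The case against.** The best reply is that the rules can be read together. The cycle-start sentence is permissive: a cycle can start, not must. A general minimum and a tighter specific rule can both be obeyed, and Table 5, being specific to drug-related liver changes, would ordinarily govern. The sentence before the general table supports this by removing liver tests from it.

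Much of that is reasonable, and a careful investigator might settle the liver case that way. But the protocol states no precedence, and the sentence after the table removes the support that the one before it gives. The instructions to follow the highest grade or the greatest reduction concern several toxicities in one patient, not several rules for one toxicity.

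For blood counts the reply is stronger. A reader might infer that a silent Grade 4 count receives flatly opposite orders. The documents do not support that. The exemption requires the abnormality to be nonclinical as well as asymptomatic, and the next paragraph acts on clinically significant hematologic toxicity. If a Grade 4 count is clinically significant, every rule agrees. Nor does footnote b cancel a delay, since it qualifies only the dose-modification column. If the sentence before the table governs, footnote b does not reach liver values at all.

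Two supports that a reader might add are weak. Section 4.3 bars growth factors from replacing a required reduction, but its example is febrile neutropenia, which is symptomatic. Section 7.5 counts Grade 4 thrombocytopenia toward suspending accrual, which is not a dosing rule.

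**Conclusion.** The point holds for liver values and, in a weaker form, for blood counts.

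- **Scope:** the two sentences around the general table contradict each other on liver tests. Under the later one, a Grade 4 ALT/AST falls under two different instructions.
- **Restart threshold:** an interrupted patient at 3 to 5 x ULN, unless at baseline, meets the cycle-start rule and not Table 5, with no stated precedence.
- **Blood counts:** an ambiguity that turns on the undefined terms nonclinical and clinically significant, not a certain contradiction.

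The restart band rests on Table 5's own grade labels, and its split by liver involvement rests on baseline being the eligibility value. The documents give no frequency for such patients and do not show that the two centers would read the text differently. After Cycle 2 the tables become guidelines, so some variation is accepted by design. Nothing here changes the 6-month PFS sample size, decision rules or error rates. The case for acting is patient safety: stated rules on holding and restarting drug should not disagree.

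**What to change.** Reconcile five pieces of section 4.2.1.1: the cycle-start sentence, footnote b, the scope sentences before and after the general table, and Table 5. Specifically:

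1. Make the two scope sentences say the same thing about liver function tests.
2. Define nonclinical and clinically significant, and state whether the laboratory exemption covers neutrophil, platelet, hemoglobin and liver values, and up to what grade.
3. Use one list of exempt laboratory abnormalities in the cycle-start sentence and footnote b, and say whether footnote b applies to interruption as well as to modification.
4. State which rule prevails when the cycle-start sentence and a specific table differ.

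Which clinical rule applies in each case is for the sponsor to decide; this review takes no position. The cost is a wording clarification confined to section 4.2.1.1, with no new assessments and no change to the statistical design.

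### Sections 4.2 and 4.2.1.1 give unranked rules for concurrent toxicities (greatest required reduction versus highest grade), and read literally they can put the same patient on doses one level (40 mg) apart

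*Combined protocol and SAP*

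**What the plan says.** Four instructions in the protocol bear on a patient with more than one toxicity.

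- Section 4.2, introductory paragraph: "Dose adjustments should be made according to the system showing the greatest degree of toxicity".
- Section 4.2.1.1, paragraph before the dose-level table: "If multiple adverse events are seen, administer dose based on greatest reduction required for any single adverse event observed".
- Section 4.2.1.1, below the dose-level table: "If a subject experience more than one toxicity, dose reduction should be according to the toxicity with the highest grade".
- The next sentence there, for toxicities of equal grade: "the investigator may dose reduce according to that deemed most causally related to study treatment".

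On how binding the tables are, section 4.2.1.1 says "Strictly follow the modification in the following tables for the first" two cycles, and treats them as guidelines afterwards.

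The toxicity-specific tables set the action for each event. In Table 3, Grade 2 HFSR that has not improved within 7 days, or is a second occurrence, carries "When resuming treatment, treat at reduced dose level"; a third occurrence carries "When resuming treatment, decrease dose by one dose level"; a fourth means discontinuation. In Table 4, Grade 3 hypertension means holding the drug until diastolic pressure is controlled and any symptoms resolve, then restarting at the same level. A cut follows only if pressure is not controlled. Footnote b of the general toxicity table exempts some toxicities from dose modification, among them non-refractory nausea or vomiting and decreased lymphocyte count.

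**The concern.** The greatest-reduction rule looks at the action each event requires. The highest-grade rule looks at severity. They agree only when the more severe event also carries the larger action, and these tables do not guarantee that: hypertension at Grade 3 can require no cut, while HFSR at Grade 2 can require one.

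Where they part, the text gives no way to choose. Two sites could each follow a stated rule and resume the same patient at different doses, and one of those doses is the full previous dose after a skin reaction whose own row asks for a reduction. This matters most in Cycles 1 and 2, when the tables are to be followed strictly. Table 3 footnote b does not permit re-escalation after an HFSR reduction, so the difference need not end with the cycle in which it arises.

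**Working it through.** **Step size.** The dose-level table lists 80, 120 and 160 mg. 160 − 120 = 40 mg and 120 − 80 = 40 mg. At 120 mg, the column for significant drug-related toxicity says "Decrease to 80 mg"; no level below 80 mg is listed.

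**The clearest pair.** Take controlled Grade 3 hypertension with Grade 2 HFSR (no improvement within 7 days, second or third occurrence). The HFSR interruption until Grade 0-1 is taken to apply under either rule, so only the resumption dose differs.

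| Current dose | Highest grade (hypertension row) | Greatest reduction (HFSR row) | Difference |
|---|---|---|---|
| 160 mg | 160 mg | 120 mg | 40 mg (40/160 = 25%) |
| 120 mg | 120 mg | 80 mg | 40 mg (40/120 = 33%) |
| 80 mg | 80 mg | no level listed | undefined |

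Over a full 21-day dosing period the gap is 40 × 21 = 840 mg. Cycle 1 reaches 160 mg only in week 3 (section 4.1), so within the two strict cycles that total at 160 mg arises only if full dosing resumes at the start of Cycle 2.

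**How far the divergence extends.** Each row of the general table, Table 3, Table 4 and Table 5 (liver) was coded by grade and by action: no cut, one level, or permanent stop. Optional cuts were coded as none, and the row for raised transaminases with raised bilirubin was coded at its lowest grade, 2. This gives 4 + 8 + 7 + 5 = 24 rows. All pairs: 24 × 23 / 2 = 276. Pairs within one table: 6 + 28 + 21 + 10 = 65. Cross-table pairs: 276 − 65 = 211.

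- *Unequal grades, lower-grade row requires the larger action:* 17 of 211. Two are the pair above, once for each of its two Table 3 rows. The other 15 have a permanent stop on the lower-grade side, such as a Grade 3 general toxicity (one level) with a fourth Grade 2 HFSR (stop). After merging identically coded rows the count is 13 of 149: one of one level and 12 stops.
- *Equal grades, actions one level apart:* 12 of the 211 pairs. The causality tie-break may then select the smaller action. Example: controlled Grade 3 hypertension (same dose) with a first Grade 3 HFSR (one level down).
- *Footnote b exemptions,* not among the 24 rows. Coding them as one Grade 3 and one Grade 4 row with no cut, and counting the two Grade 3 hypertension rows that require a cut as one, adds nine one-level conflicts. The Grade 3 exempt event conflicts with the two Grade 2 HFSR reduction rows (2). The Grade 4 exempt event conflicts with those two, first and second Grade 3 HFSR, Grade 3 hypertension requiring a cut, first Grade 3 ALT/AST, and a Grade 3 general toxicity (7). 2 + 7 = 9. Example: Grade 3 non-refractory vomiting with a second-occurrence Grade 2 HFSR.

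These are counts of table rows under a stated coding. They say nothing about how many patients are affected.

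**The case against.** The strongest reply is that the highest-grade sentence speaks of dose reduction and so presupposes that one is due. On that reading it chooses among toxicities that each call for a cut, and controlled hypertension, which calls for none, cannot cancel the HFSR cut. The text before Table 4 supports this by asking that blood pressure be controlled by means other than changing the study drug dose. The reading is reasonable and would remove the one-level conflict between the highest-grade and greatest-reduction sentences. It is not written down, however, and does not reach section 4.2, whose sentence covers dose adjustments generally.

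Several limits on consequence also stand. Table 3 is presented as recommended and suggested modification, and its footnote a always allows more conservative management, so the lower dose is never forbidden. Table 4 is introduced as suggesting reductions. After Cycle 2 all the tables are guidelines. A third HFSR occurrence within two cycles is unlikely. The significant-drug-related-toxicity column would also point to a cut if the combination counts as such, though that term is not tied to a grade.

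A reader might infer that the grade rule obliges a site to give the full dose, or lets a patient continue after a row that says stop. The documents do not support either. The lower dose is always open under Table 3, and the stop rows are worded as actions in their own right; their clash with the grade rule is literal only. A reader might equally infer that hypertension with HFSR is the sole conflict. That does not hold either once stops, exempt toxicities and equal-grade ties are considered.

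**Conclusion.** The concern holds as a minor inconsistency between stated dosing rules. Nothing ranks them, and in at least one combination short of a permanent stop they literally yield doses one level, 40 mg, apart. This assumes that the patient is at 160 or 120 mg, that blood pressure has come under control, and, for the no-improvement or second-occurrence row, that the dose was not already cut for HFSR; if it was, that row may require nothing further.

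A reader might infer a frequent problem, since section 1.2.2 lists both HFSR and hypertension among the most common grade 3 or higher events (17% and 7% in the colorectal trial; 56.1% and 48.5% in the stromal tumor trial). Those figures describe each event separately. The documents give no frequency for Grade 2 HFSR that recurs together with controlled Grade 3 hypertension, so no patient count is claimed. The two-stage decision rules, type I error, power and sample size do not depend on this point.

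**What to change.** In section 4.2.1.1, state that when several drug-related toxicities are present, the greatest reduction, or discontinuation, required by any single one of them prevails whatever the grades. Delete the highest-grade sentence there and the greatest-degree sentence in section 4.2, or make both expressly subject to that rule. Delete the causality tie-break or subordinate it in the same way. This settles the hypertension and HFSR pair, the discontinuation rows, the footnote b exemptions and the equal-grade ties together. It would also help to say what happens when a further reduction is required at 80 mg.

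The cost is one added clause and three sentences removed or subordinated at the next amendment, with no extra patients, visits or procedures. The downside is slightly lower dose intensity in patients with such combinations.
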